2.2 Analysis sets

Safety set

The Safety Set (SAF) comprises all participants who have received the 2020-2021 inactivated influenza vaccine.

Unless stated otherwise, the SAF will be used for all summary tables and listings.

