Withdrawal of study consent	Withdrawal of consent from the study occurs only when a participant does not want to participate in the study any longer and does not allow any further collection of personal data	

Amendment 3

Amendment Rationale

By the time of this amendment, it is projected that the study will not be able to enroll all planned number of patients in all three cohorts. Thus, the protocol is modified by extending the study to the next flu season (2022-2023) to allow for completing the enrollment. In addition, to continue with annual monitoring of safety and efficacy, the second interim analysis is included in this amendment.

Changes to the protocol

Changes to specific sections of the protocol are shown in the track changes version of the protocol using strike through red font for deletions and red underlined for insertions.

IRBs/IECs

A copy of this amended protocol will be sent to the Institutional Review Board (IRBs)/Independent Ethics Committee (IECs) and Health Authorities. The changes herein affect the Informed Consent. Sites are required to update and submit for approval a revised Informed Consent that takes into account the changes described in this protocol amendment.

Summary of previous amendments

Amendment 2 (15-Mar-2021)

This protocol has been modified to give participants in Cohort 2 the option to continue taking their prescribed ofatumumab during the open-label extension period of the study, correct inconsistencies related to when study drug should be administered in relation to the titer sample and to update inclusion criteria from planning to receive a 2020-2021 flu vaccine to willing to receive the 2020-2021 flu vaccine.

Amendment 1 (13-Jan-2021)

The protocol was modified to exclude participants with a history of Guillain-Barre syndrome within 6 weeks of receiving the influenza vaccination as recommended by the FDA. Additional modifications included permitting sites to administer the quadrivalent influenza vaccine from their site supply in lieu of a participant receiving it from a local pharmacy.

Protocol summary

Protocol	COMB157GUS12	
number		
Full Title	An open-label multicenter study to assess response to influenza vaccine in multiple sclerosis participants treated with ofatumumab 20 mg subcutaneously	
Brief title	A multicenter study to assess response to influenza vaccine in multiple sclerosis participants treated with ofatumumab	
Sponsor and	Novartis	
Clinical Phase	Clinical phase IV	

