The study population will consist of male and female participants, \geq 18 years of age to 55 years of age inclusive, with a diagnosis of relapsing MS.

The study aims to enroll up to 66 participants (up to 22 participants per cohort) at approximately 12 centers in the United States. Since a 25% screen failure rate is expected, approximately 88 participants will be screened.

The last day to screen a patient for this study will be when Cohort 1 and Cohort 3 each have 22 participants enrolled, or at the end of Q1 2023, whichever comes first.

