5.1 Inclusion criteria

Participants eligible for inclusion in Cohorts 1 and 2 must meet all of the following criteria:

- 1. Signed informed consent must be obtained prior to participation in the study
- 2. Age 18-55 years old
- 3. Diagnosis of relapsing MS by 2017 revised McDonald criteria
- 4. Must be willing to comply with the study schedule
- 5. Willing to receive a 2020-2021, 2021-2022, or 2022-2023 inactivated influenza vaccine
- 6. Planning to start treatment with ofatumumab or already on commercially prescribed ofatumumab for at least 2 weeks prior to the screening visit

Participants in Cohort 3 must fulfill criteria 1-5 above in addition to the following:

7. Participant must currently be receiving iDMT

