11.3 Site monitoring

Before study initiation, at a site initiation visit or at an investigator's meeting, a Novartis representative will review the protocol and data capture requirements (i.e. eCRFs) with the investigators and their staff. During the study, Novartis employs several methods of ensuring protocol and GCP compliance and the quality/integrity of the sites' data. The field monitor will visit the site to check the completeness of participant records, the accuracy of data capture / data entry, the adherence to the protocol and to Good Clinical Practice, the progress of enrollment, and to ensure that study treatment is being stored, dispensed, and accounted for according to specifications. Key study personnel must be available to assist the field monitor during these visits. Continuous remote monitoring of each site's data may be performed by a centralized Novartis CRA organization. Additionally, a central analytics organization may analyze data & identify risks & trends for site operational parameters, and provide reports to Novartis clinical teams to assist with trial oversight.

The investigator must maintain source documents for each participant in the study, consisting of case and visit notes (hospital or clinic medical records) containing demographic and medical information, laboratory data, electrocardiograms, and the results of any other tests or assessments. All information on CRFs must be traceable to these source documents in the participant's file. The investigator must also keep the original informed consent form signed by the participant (a signed copy is given to the participant).

The investigator must give the monitor access to all relevant source documents to confirm their consistency with the data capture and/or data entry. Novartis monitoring standards require full verification for the presence of informed consent, adherence to the inclusion/exclusion criteria, documentation of SAEs, and of data that will be used for all primary variables. Additional checks of the consistency of the source data with the CRFs are performed according to the study-specific monitoring plan. No information in source documents about the identity of the participants will be disclosed.

12 Data analysis and statistical methods

The analysis will be conducted on all participant data at the time the trial ends. Any data analysis carried out independently by the Investigator should be submitted to Novartis before publication or presentation.

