12.1 Analysis sets

The Safety Set comprises all participants who received at least one dose of study drug.

The Safety Set will be used for the summary of demography and baseline characteristics as well as for all safety analyses.

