12.4.2 Statistical model, hypothesis, and method of analysis

The number and percentage of responders by year of enrolment in study and overall will be presented. The 95% confidence interval for the proportion of responders will be calculated by using exact method.

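### The supplied SAP limits its only analysis set to 2020-2021 vaccine recipients, while the current protocol analyses participants from three influenza seasons

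*SAP*

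**What the plan says.** **SAP.** Section 1 says that the SAP describes the methods of protocol version 00, released 10 November 2020. Section 2.2 defines a single set: "The Safety Set (SAF) comprises all participants who have received the 2020-2021 inactivated influenza vaccine". It continues: "Unless stated otherwise, the SAF will be used for all summary tables and listings". The sections on the primary and secondary endpoints (2.5 to 2.7) name no other set. A full analysis set appears only in the abbreviation list. The 2020-2021 season recurs in the objectives (Table 1-1), treatment of interest (2.1.1), expected treatment (2.4.1), primary objective and estimand (2.5, 2.5.1), secondary objective (2.7) and the wording of deviation INCL05 (exclusion table after 5.4), which leads to exclusion from the Safety Set.

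**Protocol (amended version 03).** Inclusion criterion 5 in Section 5.1 reads "Willing to receive a 2020-2021, 2021-2022, or 2022-2023 inactivated influenza vaccine". Under Section 5, screening closes when Cohorts 1 and 3 are full "or at the end of Q1 2023, whichever comes first". The opening of Section 12 states: "The analysis will be conducted on all participant data at the time the trial ends". Section 12.4.2 adds: "The number and percentage of responders by year of enrolment in study and overall will be presented". The Safety Set in Section 12.1 has no season limit: "The Safety Set comprises all participants who received at least one dose of study drug".

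**The concern.** A programmer derives the analysis flag from the written definition. A participant vaccinated in 2021-2022 or 2022-2023 belongs in the protocol's analysis but falls outside the SAP's only set. Such participants are expected: the rationale for Amendment 3 says that "it is projected that the study will not be able to enroll all planned number of patients in all three cohorts", and enrolment was extended to the 2022-2023 season for that reason.

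The trial is purely descriptive, so its result consists of the population described and the precision of the estimates. If the SAP were followed to the letter, the reported rates would describe one season and a smaller sample. Nothing in the SAP would alert the reader, because Section 4 declares no changes to the protocol-specified analyses.

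**Working it through.** **Step 1: set the rules side by side.**

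| Item | Supplied SAP | Current protocol |
|---|---|---|
| Protocol version | 00 (Section 1) | Amended version 03 |
| Seasons | 2020-2021 | 2020-2021, 2021-2022, 2022-2023 (5.1) |
| Population for the endpoint analyses | Recipients of the 2020-2021 vaccine (2.2, by default) | All participants at trial end (opening of 12) |
| Display of responders | Number and percentage (2.5.2); no subgroup analysis (2.2.1) | By year of enrolment and overall (12.4.2) |

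A one-season set cannot supply a three-season by-year table, and its overall rate is the 2020-2021 rate. The two documents therefore give different populations for the primary estimate.

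**Step 2: check whether other SAP text repairs the definition.**
- Section 2.1 says that data up to the cut-off will be used, but the same section presents summaries on the relevant analysis set, which leads back to Section 2.2.
- The second exclusion table after Section 5.4 gives non-receipt of the influenza vaccine, with no season named, as a ground for exclusion. That does not widen the definition of who is included, and the first table still names 2020-2021.
- Section 2.3.1 summarises disposition for everyone who entered a period and screen failures for everyone screened, so those summaries are not affected.

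**Step 3: reproduce the plan's precision figures.** Protocol 12.8.1 and SAP 3 use n = 20 per cohort. The Wald half-width is 1.96 × √(p(1−p)/n):
- p = 0.70: 1.96 × √(0.21/20) = 20.1 points
- p = 0.75: 1.96 × √(0.1875/20) = 19.0 points
- p = 0.80: 1.96 × √(0.16/20) = 17.5 points

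All three match the stated 20.1, 19 and 17.5.

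**Step 4: illustrate the loss.** The documents give no enrolment by season. I assume that 0%, 25%, 50% or 75% of 20 evaluable participants in a cohort are vaccinated in later seasons. The exact (Clopper-Pearson) interval is the method planned for the analysis.

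| Left in set | Wald half-width, 70% | Wald half-width, 80% | Exact 95% interval at 80% (half-width) |
|---|---|---|---|
| 20 | 20.1 | 17.5 | 16/20: 56.3% to 94.3% (19.0) |
| 15 | 23.2 | 20.2 | 12/15: 51.9% to 95.7% (21.9) |
| 10 | 28.4 | 24.8 | 8/10: 44.4% to 97.5% (26.5) |
| 5 | 40.2 | 35.1 | 4/5: 28.4% to 99.5% (35.6) |

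The split may differ between cohorts; applying one share to a cohort of 20 is only a device to show scale.

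**The case against.** The strongest reply is that this is version lag and not an analysis choice. The supplied SAP says that it describes version 00, and its single interim is dated March 2021. One cause explains every mention of 2020-2021, the likely intent is to analyse everyone, and the current protocol already prespecifies the by-year and overall display. Much of this stands as an account of how the conflict arose. It does not remove the conflict, since the only written definition of the analysis set still excludes later seasons.

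Four stronger readings are tempting, and the documents do not support them.
- *The sponsor never updated the SAP.* This is known only for the file supplied; a later version may exist.
- *The no-changes sentence in SAP Section 4 is false.* It is measured against version 00, which is not available. It can be said only that the sentence does not hold against version 03.
- *The protocol's Safety Set fixes the primary population.* Protocol 12.1 assigns that set to demography, baseline and safety, and names no set for seroprotection. The conflict on the primary estimate is with the opening of Section 12 and with 12.4.2.
- *A known number of participants would be lost.* No season split is given, so the scenarios above are not estimates.

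**Conclusion.** The concern holds as a contradiction between the supplied SAP and the current protocol about who is analysed. Read literally, the SAP removes participants vaccinated in 2021-2022 and 2022-2023 from the seroprotection, seroconversion, demographic and adverse-event tables and makes the by-year display impossible.

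The size depends on the unknown season split. Under the assumed splits, the Wald half-width at 70% response runs from the planned 20.1 points (no loss) to 40.2 points (three quarters in later seasons). The effect is on the population described and the precision, not on error rates. The conclusion assumes that the supplied SAP is the one in force and that some participants were vaccinated after 2020-2021.

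It should be corrected before database lock, because the rule as written gives the wrong population and the correction is cheap.

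**What to change.** Amend the SAP before database lock:
1. Cite the current protocol version in Section 1.
2. In Section 2.2, define the Safety Set by receipt of the inactivated influenza vaccine of any season that the protocol permits.
3. Reword INCL05 to match current inclusion criterion 5, which concerns willingness to receive a vaccine of any of the three seasons. Keep actual receipt as the separate criterion that it already is; the two should not be merged.
4. Make the season wording consistent in Table 1-1 and Sections 2.1.1, 2.4.1, 2.5, 2.5.1 and 2.7.
5. Add the display by year of enrolment and overall from Protocol 12.4.2.
6. Restate Section 4 of the SAP against the current protocol.

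Align the interim analyses only after the protocol agrees with itself. Section 4.4 describes one interim, on or around March 31, 2022 at the latest, while Section 12.7 lists two, dated April 12, 2021 and March 31, 2022, and leaves the alternative trigger unstated. The SAP's single date of March 29, 2021 matches none of these.

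As a separate matter, align the observed-data analysis of the primary endpoint. Protocol 12.4.6 calls for it, whereas SAP 2.5.3 gives only non-responder imputation and 2.5.4 plans no supportive analyses. That gap does not follow from the season limit.

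Cost: one SAP amendment, one revised analysis-set flag and modest programming for the added tables. No new data are needed. The season correction itself needs no change to the protocol's analysis section.

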2.2.1 Subgroup of interest

There is no subgroup analysis planned for this study.

2.3 Patient disposition, demographics and other baseline characteristics

2.3.1 Patient disposition

Patient disposition will be summarized for the following study periods: screening, treatment, extension treatment and treatment assigned.

Patient disposition for each period will be summarized for all participants who entered that period. Participants who have entered any study period but have discontinued from the study will be listed as appropriate along with the primary reason for discontinuation.

The number and percentage of screening failures and the reason for screening failure will be presented for all screened participants.

For each protocol deviation, the number and percentage of participants for whom the deviation applies will be tabulated.

2.3.2 Demographics

The following demographic variables will summarized descriptively by cohort:

Continuous variables

• Age (years)

Categorical variables

- Sex (Male, Female)
- Ethnicity (Hispanic or Latino, Not Hispanic or Latino, Not reported, Unknown)
- Race (White, Black or African American, Asian (Chinese, Indian, Japanese, Korean, Vietnamese), Native Hawaiian or Pacific Islander, American Indian or Alaska Native, Multiple)

2.3.3 Medical history

Relevant medical histories and current medical conditions at baseline will be summarized by system organ class (SOC) and preferred term (PT).

Medical histories will be coded using the Medical Dictionary for Regulatory Activities (MedDRA) terminology. The latest version of which will be used for the reporting activity.

2.4 Treatments (study treatment, rescue medication, concomitant therapies, compliance)

2.4.1 Study treatment / compliance

Participants in all cohorts are expected to receive a single dose of the 2020-2021 quadrivalent inactivated influenza vaccine.

Participants in **Cohort 1** are expected to take a total of 3 of a tumumab 20 mg injections at Week 2, 3, 4 and once every 4 weeks starting at Week 6 if they chose to continue to the 6-month Extension Period.

Participants in **Cohort 2** are expected to continue on their commercially prescribed of atumumab during the Investigational Period and take study supplied of atumumab 20 mg injections once every 4 weeks thereafter if they chose to continue to the 6-month Extension Period.

Participants in **Cohort 3** are expected to continue on their commercially prescribed iDMT throughout the Investigational Period.

The number of injections of either of atumumab 20 mg, of atumumab as prescribed or iDMT as prescribed actually taken will be summarized descriptively by cohort and period (i.e. Investigational Period and Extension Period).

The summaries by cohort will be performed by the actual treatment received (as follows).

Treatment sequence:

- QIV + OMB 20mg
- QIV + OMB as prescribed
- QIV + iDMT as prescribed

Study duration

Study duration will be summarized by cohort and duration category (i.e. ≥ 1 week, ≥ 2 weeks, ≥ 3 weeks, ≥ 4 weeks, ≥ 8 weeks, ≥ 12 weeks, ≥ 24 weeks).

2.4.1.1 Visit windows

Visit windows will be used for the data that is summarized by visit; they are based on the study evaluation schedule and comprise a set of days around the nominal visit day. For any assessment, there are the protocol defined scheduled visits around which visit windows are created to cover the complete range of days within the study.

The visit windows for Cohorts 1, 2 and 3 are shown in Table 2-2, Table 2-2 and Table 2-3 respectively. These windows apply to measurements taken at every visit. For assessments collected less often different visit windows will be applied as detailed below.

When visit windows are used, all visits will be re-aligned, i.e., they will be mapped into one of the visit windows. In the case of major deviations from the visit schedule, or due to unscheduled visits, several assessments of a participant may fall in a particular visit window (either

scheduled or unscheduled). Statistical approaches to handle multiple assessments in a given visit window are specified below.

As a rule, the following steps are followed to determine the cut-offs for post-baseline time windows:

- Transform all scheduled assessment time points into study days, assuming 1 month is equal to 30.4375 days. Middle points of scheduled assessments are determined.
- The time window associated with the previous assessment ends prior to the middle point; the time window associated with the latter assessment begins after the middle point. In case the middle point is an exact study day, it will belong to the previous assessment.
- The time window of first post-baseline assessment starts with Study Day 2, unless otherwise indicated.
- For parameters, which are not collected at every visit, visit windows will be combined. For example, if a parameter is measured at Week 2 and Week 4 only, Week 2 visit window will extend from Week 2 to Week 4 (combining Week 2 and Week 4 visit windows).

Table 2-1 Visit windows for Cohort 1

Analysis visit	Time point	Scheduled visit day (study days)	Visit window (study days)
Visit 2/Baseline	Week 0	1	-7 to 1*
Visit 3	Week 2	14	2 to 17
Visit 4	Week 3	21	18 to 24
Visit 5/EOS1	Week 4	28	25 to 35
Visit 6	Week 6	42	36 to 56
Visit 7	Week 10	70	57 to 84
Visit 8	Week 14	98	85 to 112
Visit 9	Week 18	126	113 to 140
Visit 10	Week 22	154	141 to 168
Visit 11/EOS2	Week 26	182	169 to 196

^{*}Baseline measurement before vaccine administration for safety assessments.

Table 2-2 Visit windows for Cohort 2

Analysis visit	Time point	Scheduled visit day (study days)	Visit window (study days)
Visit 2/Baseline	Week 0	1	-7 to 1*
Visit 3	Week 1	7	2 to 10
Visit 4	Week 2	14	11 to 21
Visit 5/EOS1	Week 4	28	22 to 42
Visit 6	Week 8	56	43 to 70
Visit 7	Week 12	84	71 to 98
Visit 8	Week 16	112	99 to 126
Visit 9	Week 20	140	127 to 154
Visit 10	Week 24	168	155 to 182
Visit 11/EOS2	Week 28	196	183 to 210

* Baseline measurement before vaccine administration for safety assessments.

Table 2-3 Visit windows for Cohort 3

Analysis visit	Time point	Scheduled visit day (study days)	Visit windows (study days)
Visit 2/Baseline	Week 0	1	-7 to 1*
Visit 3	Week 1	7	2 to 10
Visit 4	Week 2	14	11 to 17
Visit 5	Week 3	21	18 to 24
Visit 6/EOS	Week 4	28	25 to 31

^{*} Baseline measurement before vaccine administration for safety assessments.

Multiple assessments

When there are *multiple assessments* in a particular visit window, the following rules are applied to select one value "representing" the participant in summary statistics in a visit window

- **Baseline:** The last non-missing measurement made prior to or on the date of administration of vaccine administration (the reference start date / Day 1). Only date part is considered if just one assessment on Day 1. If there are multiple assessments on Day 1, the following rules will apply:
 - a. If assessment time exists,
 - select the last available measurement prior to reference start date/time considering time;
 - If no measurement prior to reference start date/time considering time, select the earliest measurement post reference start date/time considering time.
 - b. If assessment time does not exist, select the available measurement from the lowest CRF visit number.
- **Post-baseline:** The measurement closest to the target day will be used. In the event two measurements are taken equally apart (e.g., 1 day before target date and 1 day after), the earlier one will be used. Cases where the same parameter is recorded more than once on the same date will be handled as follows:
 - a. If time of completion exists, the earliest measurement will be used;
 - b. If time does not exist, the measurement from the lowest CRF visit number will be used.

For post-baseline visit windows, the following applies (unless otherwise specified):

- For *continuous variables*, the closest to the target study day is chosen (if two assessments have the same distance, than the earlier one will be chosen).
- For *categorical variables*, identifying notable abnormalities, the record with the worst result is selected. It is noted that in the analyses performed, the worst case is clearly defined.

In case categorical variables are based on continuous variables, the visit will be assigned to the continuous variable, and this visit will be used for the derived categorical variable.

